5.5 Definitions

SERIOUS ADVERSE EVENTS

A *Serious Adverse Event (SAE)* is any untoward medical occurrence that at any dose:

- results in death
- is life-threatening (defined as an event in which the subject was at risk of death at the time of the event; it does not refer to an event which hypothetically might have caused death if it were more severe)
- requires inpatient hospitalization or causes prolongation of existing hospitalization (see **NOTE** below)
- results in persistent or significant disability/incapacity
- is a congenital anomaly/birth defect
- is an important medical event (defined as a medical event(s) that may not be immediately life-threatening or result in death or hospitalization but, based upon appropriate medical and scientific judgment, may jeopardize the subject or may require intervention [e.g., medical, surgical] to prevent one of the other serious outcomes listed in the definition above.) Examples of such events include, but are not limited to, intensive treatment in an emergency room or at home for allergic bronchospasm; blood dyscrasias or convulsions that do not result in hospitalization.)
- Potential drug induced liver injury (DILI) is also considered an important medical event.
- Suspected transmission of an infectious agent (e.g., pathogenic or nonpathogenic) via the study drug is an SAE.
- Although pregnancy, overdose, and cancer are not always serious by regulatory definition, these events must be handled as SAEs.

The following hospitalizations are not considered SAEs in this clinical trial::

- a visit to the emergency room or other hospital department < 24 hours, that does not result in admission (unless considered an important medical or life-threatening event)
- elective surgery, planned prior to signing consent
- admissions as per protocol for a planned medical/surgical procedure
- routine health assessment requiring admission for baseline/trending of health status (e.g., routine colonoscopy)
- Medical/surgical admission other than to remedy ill health and planned prior to entry into the study. Appropriate documentation is required in these cases

- Admission encountered for another life circumstance that carries no bearing on health status and requires no medical/surgical intervention (eg, lack of housing, economic inadequacy, caregiver respite, family circumstances, administrative reason).

Potential Drug Induced Liver Injury (DILI)

Wherever possible, timely confirmation of initial liver-related laboratory abnormalities should occur prior to the reporting of a potential DILI event. All occurrences of potential DILIs, meeting the defined criteria, must be reported as SAEs

Potential drug induced liver injury is defined as:

- 1) ALT or AST elevation > 3 times upper limit of normal (ULN)
AND
- 2) Total bilirubin > 2 times ULN, without initial findings of cholestasis (elevated serum alkaline phosphatase)
AND
- 3) No other immediately apparent possible causes of AST/ALT elevation and hyperbilirubinemia, including, but not limited to, viral hepatitis, pre-existing chronic or acute liver disease, or the administration of other drug(s) known to be hepatotoxic.

ADVERSE EVENTS

An Adverse Event (AE) is defined as any new untoward medical occurrence or worsening of a preexisting medical condition in a clinical investigation subject administered an investigational (medicinal) product and that does not necessarily have a causal relationship with this treatment. An AE can therefore be any unfavorable and unintended sign (such as an abnormal laboratory finding), symptom, or disease temporally associated with the use of investigational product, whether or not considered related to the investigational product.

The causal relationship to study drug is determined by a physician and should be used to assess all adverse events (AE). The causal relationship can be one of the following:

Related: There is a reasonable causal relationship between study drug administration and the AE.

Not related: There is not a reasonable causal relationship between study drug administration and the AE.

The term "reasonable causal relationship" means there is evidence to suggest a causal relationship.

Adverse events can be spontaneously reported or elicited during open-ended questioning, examination, or evaluation of a subject. (In order to prevent reporting bias, subjects should not be questioned regarding the specific occurrence of one or more AEs.)

NONSERIOUS ADVERSE EVENT

- Nonserious Adverse Events are to be provided to BMS in aggregate via interim or final study reports as specified in the agreement or, if a regulatory requirement [e.g. IND US trial] as part of an annual reporting requirement.
- Nonserious AE information should also be collected from the start of a placebo lead-in period or other observational period intended to establish a baseline status for the subjects.

A *nonserious adverse event* is an AE not classified as serious.

Nonserious Adverse Event Collection and Reporting

The collection of nonserious AE information should begin at initiation of study drug. All nonserious adverse events (not only those deemed to be treatment-related) should be collected continuously during the treatment period and for a minimum of 100 days following the last dose of study treatment.

Nonserious AEs should be followed to resolution or stabilization, or reported as SAEs if they become serious. Follow-up is also required for nonserious AEs that cause interruption or discontinuation of study drug and for those present at the end of study treatment as appropriate.

Laboratory Test Abnormalities

All laboratory test results captured as part of the study should be recorded following institutional procedures. Test results that constitute SAEs should be documented and reported as such.

The following laboratory abnormalities should be documented and reported appropriately:

- any laboratory test result that is clinically significant or meets the definition of an SAE
- any laboratory abnormality that required the subject to have study drug discontinued or interrupted
- any laboratory abnormality that required the subject to receive specific corrective therapy.

Pregnancy

If, following initiation of the investigational product, it is subsequently discovered that a study subject is pregnant or may have been pregnant at the time of investigational product exposure, including during at least 6 halflives after product administration, the investigational product will be permanently discontinued in an appropriate manner (eg, dose tapering if necessary for subject safety).

The investigator must immediately notify Worldwide Safety @BMS of this event via the Pregnancy Surveillance Form in accordance with SAE reporting procedures.

Follow-up information regarding the course of the pregnancy, including perinatal and neonatal outcome and, where applicable, offspring information must be reported on the Pregnancy Surveillance Form [provided upon request from BMS]

Any pregnancy that occurs in a female partner of a male study participant should be reported to BMS. Information on this pregnancy will be collected on the Pregnancy Surveillance Form.

Overdose

An overdose is defined as the accidental or intentional administration of any dose of a product that is considered both excessive and medically important. All occurrences of overdose must be reported as an SAE.

Other Safety Considerations

Any significant worsening noted during interim or final physical examinations, electrocardiograms, x-rays, and any other potential safety assessments, whether or not these procedures are required by the protocol, should also be recorded as a nonserious or serious AE, as appropriate, and reported accordingly.

6.0 CORRELATIVE STUDIES (APPENDIX G)

6.1 Tumor Biopsy Samples

- Tumor biopsy samples will be collected pre-therapy, at week 13, 6 months, 9 months (if clinically indicated), 12 months and at time of progression. 10 unstained slides or tumor block is required.

Contact information for tissue pickup and shipping:

[name].
Karmanos Cancer Institute
[name]
Correlative Sciences Lab Rm 808
[contact]
E-mail: [contact]

[name]
Karmanos Cancer Institute
[name]
Correlative Sciences Lab Rm 808
[contact]
Email: [contact]

Please send email with requisition form at time of submission to

[contact]

and

[contact]

6.2 Tumor Tissue Specimens (Appendix G)

Tumor tissue specimens in the form of a paraffin embedded block or a minimum of 10 unstained slides, with a single section on positively charged slides will be submitted for PD-1 and PD-L1 immunohistochemistry (IHC) assessment. These biopsy samples should be excisional, incisional, punch or core needle. Fine needle aspirates or other cytology specimens are insufficient for downstream biomarker analyses. PD-1 and PD-L1 stained tissue sections will be assessed by a pathologist and scored as positive on a 1+ to 3+ scale if membrane staining is observed.

These tumor samples, may also be assessed for the expression of other immune or related genes, RNAs and/or proteins, as well as, the presence of immune cell populations using a variety of methodologies inclusive of, but not limited to immunohistochemistry (IHC), qRT-PCR, genetic mutation detection and fluorescent in-situ hybridization (FISH). Various molecular markers with potential predictive value are currently under investigation and may be assessed in this study. These tumor tissue biomarkers include, but are not limited to PD-1, PD-L2, tumor infiltrating lymphocytes (TILs) or subpopulations of TILs and a Th1 immune mRNA expression signature. In addition, other methods of measuring tumor PD-L1 expression may also be assessed. Mutation load will be explored on tumor tissue. Tissue may be assessed for residual tumor cells and for markers expected to accompany tumor shrinkage in this study, including, but not limited to TILs and subsets thereof.

6.3 Immune response monitoring [Appendix G]

Peripheral blood (30 ml) will be drawn pre-treatment, and at following time-points (week 7 and 13, 6 months, and 12 months) after initiation of immunotherapy. The plasma and PBMC will be isolated following a standard protocol (SOP attached). In order to maintain consistent quality, all clinical sites will isolate plasma and PBMC following the exact same protocol and cryo-ship the samples to KCI for further analysis. See appendix G for details regarding sample collection and shipping. The samples should be sent to [name], contact information given below.

[name].

[name]
[name],
[name].
Cell [name] (preferred)
Ph: [contact] (Off); [contact] (Lab)
Email: [contact]

The correlative studies will focus on any phenotypic or functional changes with regards to the T cell help, cytotoxicity or regulatory characteristics as well as B cell antibody profile following immunotherapy compared to the pre-treatment samples. The plasma will be analyzed for levels of twenty-five different cytokines, chemokines and growth factors including, IFN- γ , TNF- α , MCP-1, GM-CSF, IL-1, IL-2, IL-6, IL-8 and IL-10, using a multiplex cytokine array. A multi-parametric flow cytometry will be performed for phenotypic characterization of immune cell subsets, intracellular cytokine staining in specific subsets as well as to analyze cytotoxic T cell activation. Tumor antigen-specific immune cell functional profiling will be performed via ELISPOT analysis of stimulated and non-stimulated T and B cells. While T cells will be analyzed for IFN- γ and Granzyme B secretion, B cells will be assayed for antigen-specific IgG and IgM production.

6.4 Quality of Life (QOL) Questionnaires [Appendix F]

The QOL questionnaire will be administered at the 15 time points listed in the header of the Study Calendar in Section 2.3. The FACIT symptom index score for cancer and specific bladder symptom index questionnaires will be completed at a maximum of 15 timepoints starting with pre-therapy, the days of nivolumab therapy, and then 6 and 12 month timepoints. The change in score indices will be analyzed by repeated measures analysis and modeling and will be reported.

7.0 TREATMENT PLAN, MODIFICATIONS AND CONCOMITANT THERAPY

7.1 Product Information Table

Please also see Drug Information Appendix C

The study medication (Nivolumab) will be shipped to each site by BMS.

Product Description: Nivolumab (Other names = MDX-1106, ONO-4538, anti-PD-1)					
Product Description and Dosage	Potency	Primary Packaging	Secondary Packaging	Appearance	Storage Conditions
Form		(Volume)/ (Qty)			(per label)
		Label	/Label		
		Type	Type		
Nivolumab (BMS- 936558-01)* Injection drug product is a sterile, non- pyrogenic, single-use, isotonic aqueous solution formulated at 10 mg/mL	100 mg/Vial (10 mg/mL).	Carton of 5 or 10 vials	10-cc Type 1 flint glass vials stoppered with butyl stoppers and sealed with aluminum seals.	Clear to opalescent, colorless to pale yellow liquid. May contain particles	BMS-936558-01 Injection must be stored at 2 to 8 degrees C (36 to 46 degrees F) and protected from light and freezing

*Nivolumab may be labeled as BMS-936558-01 Solution for Injection

If stored in a glass front refrigerator, vials should be stored in the carton. Recommended safety measures for preparation and handling of nivolumab include laboratory coats and gloves.

For additional details on prepared drug storage and use time of nivolumab under room temperature/light and refrigeration, please refer to the BMS-936558 (nivolumab) Investigator Brochure section for “Recommended Storage and Use Conditions”

7.2 Handling and Dispensing

The investigator should ensure that the study drug is stored in accordance with the environmental conditions (temperature, light, and humidity) as per product information and the Investigator Brochure and per local regulations. It is the responsibility of the investigator to ensure that investigational product is only dispensed to study subjects. The

investigational product must be dispensed only from official study sites by authorized personnel according to local regulations. If concerns regarding the quality or appearance of the study drug arise, the study drug should not be dispensed and contact BMS immediately.

Please refer to the current version of the Investigator Brochure and/or shipment reference sheets for additional information on storage, handling, dispensing, and infusion information for nivolumab.

Destruction

Sponsor/Investigator drug destruction is allowed provided the following minimal standards are met:

- On-site disposal practices must not expose humans to risks from the drug.
 - On-site disposal practices and procedures are in agreement with applicable laws and regulations, including any special requirements for controlled or hazardous substances.
- Written procedures for on-site disposal are available and followed. The procedures must be filed with the Sponsor SOPs and a copy provided to BMS upon request.
- Records are maintained that allow for traceability of each container, including the date disposed of, quantity disposed, and identification of the person disposing the containers. The method of disposal, ie, incinerator, licensed sanitary landfill, or licensed waste disposal vendor must be documented.
- Accountability and disposal records are complete, up-to-date, and available for BMS to review throughout the clinical trial period as per the study agreement.
- If conditions for destruction cannot be met, please contact BMS.
- It is the Sponsor Investigator's responsibility to arrange for disposal of all empty containers, provided that procedures for proper disposal have been established according to applicable federal, state, local, and institutional guidelines and procedures, and provided that appropriate records of disposal are kept.

7.3 Dose calculations and administration

Nivolumab will be given every two weeks at a dose of 240 mg to be administered as an approximately 30-60 minute +/- 10 min IV infusion.

Nivolumab Injection, 100 mg (10 mg/mL) Nivolumab injection is to be administered as an IV infusion through a 0.2-micron to 1.2-micron pore size, low-protein binding polyethersulfone membrane in-line filter at the protocol-specified doses. It is not to be administered as an IV push or bolus injection. Nivolumab injection can be infused undiluted (10 mg/mL) or diluted with 0.9% Sodium Chloride Injection, USP or 5% Dextrose Injection, USP to protein concentrations as low as .35 mg/mL. Care must be taken to assure sterility of the prepared solution as the product does not contain any antimicrobial preservative or bacteriostatic agent.

Subjects may be dosed no less than 12 days from the previous dose of drug. There are no premedications recommended for nivolumab.

Subjects should be carefully monitored for infusion reactions during nivolumab administration. If an acute infusion reaction is noted, subjects should be managed according to Appendix C.

Doses of nivolumab may be interrupted, delayed, or discontinued depending on how well the subject tolerates the treatment.

7.4 Dose Modifications

Dose reductions or dose escalations are not permitted.

7.5 Dose Delay Criteria

Because of the potential for clinically meaningful nivolumab-related AEs requiring early recognition and prompt intervention, management algorithms have been developed for suspected AEs of selected categories. [see current Investigator Brochure and Appendix D for citation examples]

Dose delay criteria apply for all therapy related adverse events (regardless of whether or not the event is attributed to nivolumab).

Nivolumab administration should be delayed for the following:

Any Grade ≥ 2 non-skin, drug-related AE, with the following exceptions:

- Grade 2 drug-related fatigue or laboratory abnormalities do not require a treatment delay
- Any Grade 3 skin, drug-related AE

Any Grade 3 drug-related laboratory abnormality, with the following exceptions for lymphopenia, leukopenia, AST, ALT, total bilirubin, or asymptomatic amylase or lipase:

- Grade 3 lymphopenia or leukopenia does not require dose delay.
- If a subject has a baseline AST, ALT, or total bilirubin that is within normal limits, delay dosing for drug-related Grade ≥ 2 toxicity.
- If a subject has baseline AST, ALT, or total bilirubin within the Grade 1 toxicity range, delay dosing for drug-related Grade ≥ 3 toxicity.
- Any Grade ≥ 3 drug-related amylase or lipase abnormality that is not associated with symptoms or clinical manifestations of pancreatitis does not require dose delay. The Investigator should be consulted for such Grade ≥ 3 amylase or lipase abnormalities.

Any AE, laboratory abnormality, or intercurrent illness which, in the judgment of the investigator, warrants delaying the dose of study medication.

Subjects who require delay of nivolumab should be re-evaluated as clinically indicated and resume nivolumab dosing when re-treatment criteria are met.

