7.6 Criteria to Resume Treatment

Subjects may resume treatment with study drug when the drug-related AE(s) resolve to Grade ≤ 1 or baseline value, with the following exceptions:

- Subjects may resume treatment in the presence of Grade 2 fatigue
- Subjects who have not experienced a Grade 3 drug-related skin AE may resume treatment in the presence of Grade 2 skin toxicity
- Subjects with baseline Grade 1 AST/ALT or total bilirubin who require dose delays for reasons other than a 2-grade shift in AST/ALT or total bilirubin may resume treatment in the presence of Grade 2 AST/ALT OR total bilirubin
- Subjects with combined Grade 2 AST/ALT AND total bilirubin values meeting discontinuation parameters should have treatment permanently discontinued
- Drug-related pulmonary toxicity, diarrhea, or colitis, must have resolved to baseline before treatment is resumed. *Subjects with persistent Grade 1 pneumonitis after completion of a steroid taper over at least 1 month may be eligible for retreatment if investigator allows, but should be discussed with the PI.*
- Drug-related endocrinopathies adequately controlled with only physiologic hormone replacement may resume treatment *if investigator allows, but should be stated in the protocol clearly.*

If the criteria to resume treatment are met, the subject should restart treatment at the next scheduled timepoint per protocol.

If treatment is delayed or interrupted for > 6 weeks, the subject must be permanently discontinued from study therapy, except as specified in discontinuation section.

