7.7 Management Algorithms

Guidelines for the management of immune related events can be found in the current Investigator Brochure AND in the approved USPI in the US. Investigators should decide the appropriate source of AE management for each protocol.

Immuno-oncology (I-O) agents are associated with AEs that can differ in severity and duration than AEs caused by other therapeutic classes. Nivolumab is considered an

immuno-oncology agent in this protocol. Early recognition and management of AEs associated with immuno-oncology agents may mitigate severe toxicity. Management algorithms have been developed to assist investigators in assessing and managing the following groups of AEs:

Gastrointestinal, Renal, Pulmonary, Hepatic, Endocrinopathies, Skin, Neurological.

For subjects expected to require more than 4 weeks of corticosteroids or other immunosuppressants to manage an AE, consider recommendations provided in the algorithms. These algorithms are found in the Nivolumab IB [and in Appendix G] of this protocol. The guidance provided in these algorithms should not replace the Investigator's medical judgment but should complement it.

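### Section 7.5 does not require a dose delay for a Grade 2 drug-related creatinine rise recorded as a laboratory abnormality, Appendix C says to withhold and give steroids, and nothing says which governs

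*Combined protocol and SAP*

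**What the plan says.** **Section 7.5.** Dosing is delayed for any Grade 2 or higher "non-skin, drug-related AE, with the following exceptions". The first exception reads "Grade 2 drug-related fatigue or laboratory abnormalities do not require a treatment delay". Other laboratory abnormalities trigger a delay from Grade 3. A few analytes have their own rules, and only the liver tests can bring the trigger down to Grade 2: "If a subject has a baseline AST, ALT, or total bilirubin that is within normal limits, delay dosing for drug-related Grade" 2 or higher. Creatinine is not named. The section closes with a discretionary clause: "Any AE, laboratory abnormality, or intercurrent illness which, in the judgment of the investigator, warrants delaying the dose of study medication".

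**Appendix C, nephritis and renal dysfunction.** Nivolumab is withheld for a Grade 2 or 3 increase in serum creatinine and stopped for Grade 4. Corticosteroids are given for Grades 2 to 4.

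**Appendix D, same heading.** The dose is withheld when creatinine is above 1.5 and up to 6 times ULN.

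**Which source applies.** Section 7.5 mentions Appendix D only in a bracket: "see current Investigator Brochure and Appendix D for citation examples". Section 7.7 says "Investigators should decide the appropriate source of AE management for each protocol", describes the algorithms as complementing medical judgment, and locates them in the Investigator Brochure and Appendix G. Appendix C calls itself guidance and refers to the approved label where applicable.

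**Restart.** Section 7.6: "Subjects may resume treatment with study drug when the drug-related AE(s) resolve to Grade" 1 or less, or to the baseline value, and then "If the criteria to resume treatment are met, the subject should restart treatment at the next scheduled timepoint per protocol".

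**The concern.** Section 4.2 requires creatinine within 72 hours before each re-dosing, so the question arises at the dosing decision itself. For the same drug-related Grade 2 value, a site reading Section 7.5 may give the infusion, while a site reading Appendix C holds it and starts steroids. The first site has followed one part of the protocol and departed from another.

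This is a patient-safety matter. Appendix C lists nephritis as an immune-mediated risk of nivolumab. Inclusion criterion 5b makes a creatinine clearance of 60 ml/min or less a qualifying reason for entry, and criterion 13 can admit patients with clearance just above 40. These patients have little renal reserve. Section 1.5 expects two or three sites besides the coordinating center, so practice could differ between sites.

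**Working it through.** The check is a comparison of texts. The plan states no figure on this point that could be reproduced, apart from the background rate in step 4.

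**Step 1. Set the instructions side by side for a drug-related creatinine rise.**

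| Event | Sections 7.5 and 7.8 | Appendix C | Agree? |
|---|---|---|---|
| Grade 2, recorded as a laboratory abnormality | No delay required; delay allowed on judgment | Withhold; steroids | No |
| Grade 2 nephritis, recorded as a clinical event | Delay (general rule in 7.5) | Withhold; steroids | Yes, on the hold |
| Grade 3 laboratory abnormality | Delay (7.5) | Withhold; steroids | Yes, on the hold |
| Grade 4 laboratory abnormality | Stop (7.8; creatinine is not among its exceptions) | Stop; steroids | Yes, on stopping |

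Only the first row conflicts. On steroids for creatinine, Section 7 is silent, which is not a contradiction.

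**Step 2. Place Appendix D.** It uses multiples of ULN and not grades. How far its range overlaps Grade 2 depends on the CTCAE cut-points, which the documents do not give. Appendix C, which is written by grade, therefore carries the conflict, and Appendix D is supporting evidence.

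**Step 3. Look for an order of precedence.** Sections 7.5 and 7.7 and the opening of Appendix C all touch on the source of management. None says what to do when 7.5 and an appendix differ. Appendix G, to which 7.7 points, is used in Section 6 for correlative studies. It is not in the text available for this review, so whether it also holds algorithms cannot be checked.

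**Step 4. Frequency.** Appendix C gives 23/1994 = 0.0115, which it rounds to 1.2%. That numerator counts immune-mediated nephritis and renal dysfunction under monotherapy. It is not split by grade, and it would not capture drug-related Grade 2 rises that were never classed as immune-mediated. Multiplying it by the 34 planned patients would not estimate the disputed event, so no expected count is given.

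**Step 5. Exposure per event.** Assume that the rise is found on a dosing day (day 0) and that dosing is every 14 days.
- Dosing on under 7.5: 0 doses held.
- Hold with restart under 7.6, recovery by day 14: the day 0 dose is held, so 1 of at most 14.
- Hold with restart under 7.6, recovery by day 28: days 0 and 14 are held, so 2 of at most 14.
- Recovery by day 14, and the investigator chooses to wait for a taper of at least 28 days: 14 + 28 = day 42. Days 0, 14 and 28 are held, so 3 of at most 14. Counted from the held dose, a restart after day 42 exceeds six weeks and needs the steroid-taper exception in 7.8.

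**The case against.** The best defence is that the exemption is permissive. It says that a delay is not required, and the closing clause of 7.5 lets the investigator delay for any laboratory abnormality. An investigator who withholds therefore complies with 7.5 and both appendices at once. Section 7.5 also refers the reader to Appendix D, and 7.7 lists renal events among the algorithm groups. This stands, and it limits the point. A reader might infer that the protocol obliges sites to dose through a Grade 2 creatinine rise. It does not. What remains is that a site may dose on and still comply with 7.5, because discretion does not replace the trigger stated in Appendix C.

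A second defence is that Section 5.1 records a laboratory value as an adverse event once it needs clinical intervention or changes therapy, so that a rise treated under Appendix C would be held under the general rule in 7.5. This helps where the event is handled as nephritis. Otherwise it is circular: the value qualifies because someone has already decided to act. The laboratory exemption is, moreover, itself an exception to the adverse-event rule.

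A third is that Appendix C, or the label, was meant to govern. That may be the intention, but the words used are guidance and where applicable, and 7.7 leaves the choice of source to investigators.

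**Conclusion.** The inconsistency is real and should be corrected. It is confined to a drug-related Grade 2 creatinine rise handled as a laboratory abnormality. For that event Section 7.5 requires no delay, Appendix C directs a hold with steroids, and neither is said to prevail. The comparison with Appendix C rests on the text alone; the Appendix D overlap needs CTCAE cut-points from outside the documents.

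The size is one or two held doses per event if restart follows 7.6, under the timing assumptions above, against none if dosing continues. How often the event will occur in this population is unknown.

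Three stronger readings are tempting but not supported:
- A reader might take 1.2% as a ceiling on affected patients. It counts a different event in a different population.
- A reader might conclude that restart must wait for a completed taper. Appendix C says so only as something to consider, under its heading for other immune-mediated reactions, and its nephritis text sets no such condition.
- A reader might expect harm to the sample size, the significance level or the analysis set. Nothing in the documents links this point to them.

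**What to change.** 1. Add to the exceptions in 7.5: *Creatinine: delay dosing for a drug-related rise to Grade 2 or higher that is a worsening from baseline, and manage it per Appendix C, including corticosteroids; resume per 7.6 (Grade 1 or less, or baseline value).* The baseline wording is needed because criterion 13 accepts either creatinine up to 1.5 times ULN or clearance above 40 ml/min. A patient can therefore enter already above the Appendix D threshold.
2. Add to 7.7: *Where Section 7.5 and Appendices C or D differ on withholding nivolumab for a drug-related creatinine rise from baseline, the more conservative instruction applies.* Restart stays with 7.6.
3. In 7.7, add a pointer to Appendix D. Keep the Appendix G pointer, since its content could not be checked.

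Do not make completion of a steroid taper a condition for restart; leave it to the investigator, as Appendix C does. Leave the package-insert table in Appendix D and the eligibility criteria as they are.

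The cost is two sentences and one cross-reference in an amendment. The downside is a few more Grade 2 holds, each costing at least one scheduled dose, which the appendices already direct. Eligibility, accrual and analysis do not change.
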